6.2. Preparation/Handling/Storage/Accountability

- Bottles containing GB004 tablets or placebo will be shipped to clinical sites using temperature monitoring devices and stored at 2°C to 8°C. The Investigator or designee must confirm appropriate temperature conditions have been maintained during transit for all IP received and any discrepancies are reported and resolved before use of the IP.
- Only randomized subjects may receive IP and only authorized site staff may supply IP. At the study site, all IP must be stored in a secure, refrigerated (2°C to 8°C), environmentally controlled, and monitored (manual or automated) area in accordance with the labeled storage conditions with access limited to the Investigator and authorized site staff.
- Subjects will be provided with coolers for transport of IP from the study site to their home location. Once at home, IP is to be stored in a refrigerator.
- The Investigator, institution, or the head of the medical institution (where applicable) is responsible for IP accountability, reconciliation, and record maintenance (ie, receipt, reconciliation, and final disposition records).

6.3. Measures to Minimize Bias: Randomization and Blinding

6.3.1. Assignment of a Subject Number

At the Screening visit, a unique subject number will be assigned to a subject upon signing of the ICF.

6.3.2. Randomization and Stratification

At PCP Day 1/Week 0 visit, all subjects who meet eligibility criteria will be centrally randomized 1:1:1 to GB004 480 mg BID, GB004 480 mg QD, or placebo using an interactive response technology (IRT) system.

Before the study is initiated, directions for use of the IRT system will be provided to the sites.

Randomization will be stratified by systemic corticosteroid use at baseline (yes/no).

6.3.3. Investigational Product Numbers

IP will be dispensed at the study visits as summarized in the SoA (Section 1.3.1 – PCP and Section 1.3.2 – OLE). On PCP Day 1/Week 0 visit, the IRT system will assign IP bottle number(s) based on the subject's randomized treatment group.

For subsequent visits when IP is dispensed, the IRT system will assign new IP bottle number(s) based on the subject's randomized/assigned treatment group.

6.3.4. Blinding

Subjects, investigators and site personnel, and the Sponsor (with exceptions described below) will be blinded to individual subject treatment assignments in the PCP. All subjects will dose IP BID to maintain the blind.

The study will be unblinded to the Sponsor at the time of the PCP Week 12 Analysis (see Section 9.4). Therefore, the PCP will be double-blind through PCP Week 12 and will remain blinded to subjects, investigators, and site staff throughout the PCP.

Sponsor (or designee) personnel will have access to unblinded individual subject treatment assignments for the purposes of study-required activities, including management of IP inventory, production of summaries of data for DRC review, and performance of bioanalytical analysis of PK and gene/protein concentrations. These personnel will not be directly involved in the conduct of the study.

A DRC will periodically convene to review unblinded overall safety and emerging efficacy results (refer to Section 9.5.1).

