6.5. Dose Modification

6.5.1. Investigational Product

Dose modification, as described below, may be considered for treatment-related AEs and liver chemistry laboratory abnormalities.

Dose reduction will be prescribed in two steps (as detailed in the Study Reference Manuals):

- First reduction step: IP dose will be reduced by 2 tablets BID
- Second reduction step (only if either treatment-related AE or liver function abnormality persist for 7 days following initiation of first step of dose reduction): IP dose will be reduced further by 1 tablet BID

Treatment-related AEs (other than liver chemistry laboratory abnormalities described below):

Dose modification of IP may be undertaken only after consultation and approval from the Sponsor's Medical Monitor (or designee) for AEs assessed by the Investigator as treatment-related, such as tolerability related AEs. Subjects may be requested to attend an unscheduled visit after dose reduction (before potential re-administration of IP at a higher dose as described below), to collect blood samples for safety and PK, if possible.

Liver chemistry laboratory abnormality:

- Dose modification of IP may be undertaken only after consultation and approval from the Sponsor's Medical Monitor (or designee) for confirmed ALT or AST $\geq 3 \times$ ULN and $< 5 \times$ ULN meeting the criterion described in [Table 6](#) in [Appendix 7](#).
- For confirmed ALT or AST $\geq 3 \times$ ULN meeting criteria in [Table 7](#) in [Appendix 7](#), IP should be discontinued.

In both study periods, following dose reduction, IP may be re-administered at a higher dose in consultation with the Sponsor's Medical Monitor (or designee).

After consultation and approval from the Sponsor's Medical Monitor (or designee), subjects with a dose reduction during the PCP may enter the OLE at the reduced dose (reduced number of tablets as specified above) or at full dose (480 mg BID).

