9. STATISTICAL CONSIDERATIONS

9.1. Statistical Hypotheses

9.1.1. Placebo-Controlled Period

The PCP is designed to demonstrate the superiority of each GB004 treatment group to placebo on the primary endpoint of the proportion of subjects with clinical remission at PCP Week 12. The PCP is also designed to demonstrate the superiority of each GB004 treatment group to placebo on the primary endpoint of the proportion of subjects with clinical remission at PCP Week 36.

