9.4. Statistical Analyses

Three separate formal statistical analyses will be performed:

- The PCP Week 12 Analysis will be conducted after all subjects either complete the PCP Week 12 visit or withdraw from the study prior to completion of the PCP Week 12 visit. This analysis will evaluate endpoints at or up through PCP Week 12.
- The PCP Final Analysis will be conducted after all subjects either complete the PCP or withdraw from the study prior to completion of the PCP; This analysis will evaluate all PCP endpoints.
- The OLE Final Analysis will be conducted after all subjects either complete the OLE period or withdraw from the study prior to completion of the OLE period.

The study will be unblinded to the Sponsor at the time of the PCP Week 12 Analysis. Therefore, the PCP will be double-blind through PCP Week 12 and will remain blinded to subjects, investigators, and site staff throughout the PCP.

In general, continuous variables will be summarized using the number of subjects with non-missing data, mean, standard deviation, standard error (where appropriate), median, minimum, and maximum. Categorical variables will be summarized using counts and percentages.

For the PCP Week 12 Analysis and the PCP Week 36 Analysis, baseline will be defined as the last non-missing value prior to first dose of IP in the PCP. For the OLE Analysis, GB004 baseline will be defined as the last non-missing value prior to the first dose of GB004 in the study.

This section is a summary of the planned statistical analyses of the primary, secondary, and safety endpoints.

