
 Immediately interrupt IP. Report the event to the Sponsor's Medical Monitor (or designee) within 24 hours. Repeat liver chemistry tests (include ALT, AST, GGT, ALP, total bilirubin, direct bilirubin, and INR) and perform the Liver Safety Laboratory Assessments (Table 5) within 24 hours. If the repeat liver chemistry test confirms the criteria are met, monitor the subject until liver chemistry test abnormalities resolve, stabilize, or return to baseline after discussion with the Sponsor's Medical Monitor (or designee) (see MONITORING). Do not restart IP unless Sponsor's Medical Monitor (or designee) approval is granted. If restart is granted, IP may be restarted at modified dose (Section 6.5.1). If restart not granted, permanently discontinue IP and continue subject in the study for any protocol specified follow up assessments. Complete an SAE data collection tool if the event also met the criteria for an SAE.^b Liver imaging (ultrasound, magnetic resonance, or computerized tomography), liver biopsy, and/or specialist consultation to evaluate liver disease may be requested by the Sponsor. 	
MONITORING	
If ALT or AST $\geq 3 \times$ ULN AND bilirubin $> 2 \times$ ULN or INR > 1.5:	If ALT or AST $\geq 3 \times$ ULN AND bilirubin $\leq 2 \times$ ULN and INR ≤ 1.5:

 Monitor subject twice weekly until liver chemistry test abnormalities resolve, stabilize, or return to baseline. 	
 Monitor subjects weekly until liver chemistry abnormalities resolve, stabilize, or return to baseline.

^a Serum bilirubin fractionation should be performed if testing is available. If serum bilirubin fractionation is not immediately available, discontinue IP if ALT or AST $\geq 3 \times$ ULN **and** bilirubin $> 2 \times$ ULN. Additionally, if serum bilirubin fractionation testing is unavailable, **record the absence/presence of detectable urinary bilirubin on dipstick** which is indicative of direct bilirubin elevations suggesting liver injury.

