2.5.2. Blinding

The PCP is considered double-blind through PCP Week 12, as the study will be unblinded to the Sponsor at the time of the PCP Week 12 Analysis. The Sponsor (with exceptions described below) will be blinded to individual subject treatment assignments until the PCP Week 12 Analysis. Subjects, investigators and site personnel, personnel performing central endoscopic and histologic evaluations, and personnel performing central laboratory and ECG evaluations will remain blinded to individual subject treatment assignments throughout the PCP.

Sponsor (or designee) personnel will have access to unblinded individual subject treatment assignments prior to unblinding of the Sponsor at the time of the PCP Week 12 Analysis for the purposes of study-required activities, including management of IP inventory, production of summaries of data for DRC review, performance of bioanalytical analysis of PK and gene/protein concentrations, and performance of population pharmacokinetic modeling, for which subject level treatment assignment data will be provided to clinical pharmacology personnel performing the modeling using only pseudonymized (also known as dummy) subject identifiers. These personnel will not be directly involved in the conduct of the study. The DRC, comprised of Sponsor representatives not directly involved in the conduct of the study and external expert physicians, will have access to unblinded study results and data during the course of the study.

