 - This ICE is considered to have occurred on the first date of qualifying dose increase.
- Post-baseline prolonged course of systemic corticosteroids, where ‘prolonged’ is defined as consecutive use for > 7 days, for an indication other than UC.

This ICE is considered to have occurred on the first start date of qualifying systemic corticosteroid use.

- A colectomy (partial or total) or an ostomy.

This ICE is considered to have occurred on the procedure date for the colectomy or ostomy.

- Discontinuation of PCP study treatment > 28 days prior to the timepoint of the endpoint.

The approach for handling intercurrent events described above will be applied prior to employing the approaches for handling of missing data described in [Section 8.1.1](#) above.

Identification of ICEs may be performed by programmatic derivation and/or manual review. For the PCP Week 12 Analysis, this will be performed prior to Sponsor unblinding.

The number and percentage of subjects with an ICE will be summarized overall and by each of the types of ICEs listed above. For the PCP Final Analysis, this will be further summarized with respect to ICE occurrence prior to PCP Week 12. A by-subject data listing of ICEs will be provided.

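### The Sponsor is unblinded at the Week 12 Analysis, and neither document keeps the Medical Monitor blinded for subjects not yet at Week 36

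*Protocol*

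**What the plan says.** **Unblinding.** Protocol 6.3.4: "The study will be unblinded to the Sponsor at the time of the PCP Week 12 Analysis". SAP 2.5.2 says that the Sponsor "will be blinded to individual subject treatment assignments until the PCP Week 12 Analysis". It then lists those who stay blinded throughout the placebo-controlled period (PCP): subjects, investigators and site personnel, central endoscopy and histology readers, and central laboratory and ECG personnel. No Sponsor role is on that list.

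**Separation rule.** Sponsor staff given codes for specified tasks (IP inventory, summaries for the data review committee, bioanalysis and, in the SAP, PK modelling) are covered by this sentence: "These personnel will not be directly involved in the conduct of the study". The general unblinding at Week 12 carries no such condition.

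**Timing.** Protocol 9.4: "The PCP Week 12 Analysis will be conducted after all subjects either complete the PCP Week 12 visit or withdraw from the study" before that visit. Treatment runs to Week 36.

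**Medical Monitor (or designee).**
- Approves dose reductions (Protocol 6.5.1; Appendix 7, Table 6).
- Approves restart after a liver interruption (Appendix 7, Table 7): "Do not restart IP unless Sponsor's Medical Monitor (or designee) approval is granted". If restart is not granted, IP is permanently discontinued.
- Is consulted on re-escalation (6.5.1), on continuing or stopping IP for immediate safety concerns (opening of Section 8) and, if possible, on changes to background UC therapy (6.5.2).

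**Week 36 endpoint.** Protocol 9.1.1: "The PCP is also designed to demonstrate the superiority of each GB004 treatment group to placebo" on clinical remission at Week 36, which Sections 3.1 and 9.2.1 list as secondary. SAP 8.1.4 treats this event as failure to meet a binary endpoint: "Discontinuation of PCP study treatment > 28 days prior to the timepoint of the endpoint". The SAP promises that intercurrent events will be identified before Sponsor unblinding for the Week 12 Analysis only.

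**The concern.** The plan separates the few staff who hold codes early from study conduct, but states no separation once the Sponsor as a whole is unblinded. From then on, the person who approves or refuses a restart may know both the subject's arm and the Week 12 result. Blinding the sites does not remove this, because the decision comes to the site from the Sponsor.

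What is at stake is the Week 36 comparison and the pattern of discontinuation by arm after Week 12. If restarts or continue/stop advice differed by arm, even without intent, the 28-day rule would turn that difference into a difference in non-response. The same unblinded Sponsor could also be classifying Week 36 intercurrent events, some of them by manual review.

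**Working it through.** **1. The plan's own figure.** The plan claims about 80% power per comparison (10% vs 30.4%, two-sided 0.050, about 65 per group, 8% dropout by Week 12) and restates it for Week 36. Evaluable subjects per group: 65 × 0.92 = 59.8, about 60. The pooled chi-squared formula at 60 per group gives 80.3%. The figure reproduces and is not in dispute.

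**2. Which decisions reach the Week 36 endpoint.**

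| Medical Monitor role | Type of role | Route to Week 36 status |
|---|---|---|
| Restart after liver interruption | Approval | Direct: refusal is permanent discontinuation; non-response if more than 28 days before Week 36 |
| Continue or stop IP for safety | Discussion | Direct, through the same 28-day rule |
| Dose reduction | Approval | Indirect: not an intercurrent event in SAP 8.1.4 |
| Re-escalation | Consultation | Indirect: not an intercurrent event |
| Background UC therapy change | Discussion, if possible | Weak: a qualifying increase is an intercurrent event, but the Medical Monitor does not decide it |
| Extension entry dose after a PCP reduction | Approval | None: SAP 3.1.2 takes data only up to the first extension dose |

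**3. How many subjects are still in the window.** Accrual time T and the lag L from the last Week 12 visit to unblinding are not stated, so both are assumptions. With uniform accrual, the share still in Weeks 12 to 36 is (24 − L)/T.

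| T (weeks) | L = 0 | L = 8 |
|---|---|---|
| 52 | 24/52 = 46% (90 of 195) | 16/52 = 31% (60) |
| 78 | 24/78 = 31% (60) | 16/78 = 21% (40) |
| 104 | 24/104 = 23% (45) | 16/104 = 15% (30) |

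These shares are before dropout and early extension entry. SAP 8.2 also restricts Week 36 analyses to subjects who consented to protocol version 2.0, so 195 is an upper base. They count subjects in the window, not subjects who face a decision.

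**4. How many face a restart decision.** The table implies 10 to 30 subjects per arm (30/3 to 90/3). Assume that 2% to 10% of them have a liver interruption; the documents give no rate.
- Events per arm: 10 × 0.02 = 0.2 to 30 × 0.10 = 3.
- Placebo responders lost if every restart were refused, at 10% remission: 0.02 to 0.3.
- Responders lost in a GB004 arm, at 30.4%: 0.06 to 0.9.

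Continue/stop discussions would add to this by an amount that the documents do not allow me to estimate.

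**5. What such losses would do.** Exact binomial calculation with 65 per group, no true difference and an unstratified pooled test. GB004 has rate p, placebo has p − k/65, and k is the expected number of placebo responders lost. The table gives the chance of a false result favouring GB004.

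| k | p = 10% | p = 20% |
|---|---|---|
| 0 | 2.5% | 2.4% |
| 0.3 | 3.1% | 2.8% |
| 1 | 4.9% | 4.0% |
| 2 | 9.2% | 6.4% |
| 3 | 16.4% | 9.8% |

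The test is sensitive to one or two subjects, but the restart route alone, under the assumptions in step 4, supplies at most about 0.3 placebo responders at p = 10%.

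**The case against.** The design is disclosed: both documents call only the first 12 weeks double-blind. The SAP was final before unblinding, outcome scoring stays blinded, and Week 36 remission is a secondary endpoint of a Phase 2 trial tested without multiplicity adjustment. Liver interruption is triggered largely by laboratory thresholds, and screening excludes ALT or AST above 1.5 × ULN, so restart decisions should be few. The designee could be a blinded outside monitor, and access limits may sit in an operational plan not available here.

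All of this stands as a limit on size. None of it supplies the missing statement: the documents set an unblinding rule for the Sponsor and name no exception for those who act on individual subjects.

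A reader might go further, and the documents do not support it:
- **That the Medical Monitor will know every assignment.** The text permits this; it does not say that it will happen.
- **That the Medical Monitor approves re-escalation.** Section 6.5.1 provides for consultation only.
- **That all the listed decisions feed directly into Week 36 status.** Dose changes act only indirectly, and the extension entry dose cannot affect PCP endpoints.
- **That 45 to 90 subjects are biased.** That is the number in the window with no analysis lag, not the number facing a decision.

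**Conclusion.** The gap is real but limited. After the Week 12 Analysis nothing in either document keeps the Medical Monitor (or designee) or the study team blinded to individual assignments, while that role can still determine whether a subject not yet at Week 36 stays on IP. Blinded identification of intercurrent events for Week 36 is not promised either.

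Under the stated accrual and lag assumptions, about 15% to 46% of subjects are in the window, and very few of them would need a decision. The likely bias in the Week 36 comparison is small. A reader might conclude that the Week 36 result is invalid, or that the Week 12 result is compromised; neither follows. The primary endpoint is complete before the Sponsor is unblinded. The change is still worth making because the Week 36 comparison carries a superiority claim and the safeguard is inexpensive.

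**What to change.** 1. In Protocol 6.3.4 and SAP 2.5.2, limit access to individual assignments from the Week 12 Analysis to a listed Sponsor group not directly involved in study conduct, the condition that the plan already applies to its early code-holders.
2. State there that the Medical Monitor (or designee), site-facing staff and data management stay blinded to individual assignments until PCP Final database lock, except for emergency unblinding and SUSAR reporting.
3. In SAP 8.1.4, require intercurrent events for the PCP Final Analysis to be identified by staff blinded to assignment.

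The cost is a paragraph in each document, an access list, and a firewall kept for up to about 24 more weeks. The Week 12 readout is not delayed, and no dose, restart or stopping rule changes.

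Separately, the sponsor should reconcile the text on the Table 7 liver criteria. Protocol 6.5.1 says that IP should be discontinued, while Section 7.1.3 and Appendix 7 describe interruption with possible restart. How many restart decisions arise depends on which text governs.

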6.3.5. Unblinding of an Individual Subject

The IRT system will be programmed with blind-breaking instructions. In case of a medical emergency, the Investigator has the sole responsibility for determining if unblinding of a subject's treatment assignment is warranted. Subject safety must always be the first consideration in making such a determination. If the Investigator decides that unblinding is warranted, the Investigator, when possible, should make every effort to contact the Sponsor to discuss unblinding a subject's treatment assignment unless this could delay medical emergency treatment of the subject. If a subject's treatment assignment is unblinded, the Sponsor must be notified within 24 hours after breaking the blind. The date and reason that the blind was broken must be recorded in the source documentation.

Appropriate personnel at the Sponsor will unblind suspected unexpected serious adverse reactions (SUSARs) for the purpose of regulatory reporting. The Sponsor will submit SUSARs to Regulatory Agencies in blinded or unblinded fashion according to local law. The Sponsor will submit SUSARs to Investigators in a blinded fashion.

6.4. Investigational Product Compliance

The first dose of IP will be administered in the clinic on PCP Day 1/Week 0 with food. All subsequent doses will be taken at home with food with the exception of the morning doses at the PCP Week 2, 4, 8, 12, and 36 visits and OLE Enrollment, Week 2, 12 and EOT visits where IP will be administered in the clinic, with food, after pre-dose blood collection as specified in the SoA (Section 1.3.1 – PCP and Section 1.3.2 – OLE).

After initiation of IP on PCP Day 1/Week 0 visit, subjects will visit the clinic for assessments of IP use as specified in the SoA (Section 1.3.1 – PCP and Section 1.3.2 – OLE). IP accountability will be assessed by counting returned tablets. Subjects who demonstrate poor IP compliance should be re-educated on the importance of taking their medications as prescribed.

Subjects will be asked to record dosing information on a daily basis in an eDiary.

For additional details refer to Study Reference Manuals.

Guidance for Missed Dose(s)

If a dose is missed, subjects should be instructed to skip the missed dose if there are less than 6 hours before the time of the next dose, resume dosing at their next scheduled dosing time, and document the missed dose.

6.5. Dose Modification

6.5.1. Investigational Product

Dose modification, as described below, may be considered for treatment-related AEs and liver chemistry laboratory abnormalities.

Dose reduction will be prescribed in two steps (as detailed in the Study Reference Manuals):

- First reduction step: IP dose will be reduced by 2 tablets BID
- Second reduction step (only if either treatment-related AE or liver function abnormality persist for 7 days following initiation of first step of dose reduction): IP dose will be reduced further by 1 tablet BID

Treatment-related AEs (other than liver chemistry laboratory abnormalities described below):

Dose modification of IP may be undertaken only after consultation and approval from the Sponsor's Medical Monitor (or designee) for AEs assessed by the Investigator as treatment-related, such as tolerability related AEs. Subjects may be requested to attend an unscheduled visit after dose reduction (before potential re-administration of IP at a higher dose as described below), to collect blood samples for safety and PK, if possible.

Liver chemistry laboratory abnormality:

- Dose modification of IP may be undertaken only after consultation and approval from the Sponsor's Medical Monitor (or designee) for confirmed ALT or AST $\geq 3 \times$ ULN and $< 5 \times$ ULN meeting the criterion described in [Table 6](#) in [Appendix 7](#).
- For confirmed ALT or AST $\geq 3 \times$ ULN meeting criteria in [Table 7](#) in [Appendix 7](#), IP should be discontinued.

In both study periods, following dose reduction, IP may be re-administered at a higher dose in consultation with the Sponsor's Medical Monitor (or designee).

After consultation and approval from the Sponsor's Medical Monitor (or designee), subjects with a dose reduction during the PCP may enter the OLE at the reduced dose (reduced number of tablets as specified above) or at full dose (480 mg BID).

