7.1.3. Liver Function: Actions and Follow-up Assessments

Liver chemistry will be evaluated as specified in the SoA (Section [1.3.1](#) – PCP and Section [1.3.2](#) – OLE).

For ALT or AST $\geq 3 \times$ ULN, refer to [Appendix 7](#) for guidelines on monitoring and criteria for possible dose modifications (Section [6.5.1](#)) and temporary interruption of IP with possible restarting criteria and actions.

Any occurrence of a confirmed ALT or AST value $\geq 3 \times$ ULN will be monitored and evaluated for an etiology (for example viral hepatitis, drug and herbal supplements, environmental exposure, alcohol use, and other) in consultation with the Sponsor ([Appendix 2](#), [Table 5](#)).

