ALT or AST $\geq 3 \times$ ULN and $< 5 \times$ ULN AND bilirubin $\leq 2 \times$ ULN AND without symptoms believed to be related to liver injury or hypersensitivity^a AND who can be monitored weekly for 4 weeks	
 Notify the Sponsor's Medical Monitor (or designee) within 24 hours of learning of the abnormality to discuss subject safety. “Liver Safety Laboratory Assessment” in Table 5 may be requested by the Sponsor's Medical Monitor (or designee). Confirm values within 24-48 hours via repeat laboratories (include ALT, AST, GGT, ALP, total bilirubin, direct bilirubin, and INR). If unable to obtain repeat laboratories within 24-48 hours, decision to continue or interrupt IP will be determined by the Investigator in consultation with the Sponsor's Medical Monitor (or designee). If repeat laboratories confirm that criteria are met, the dose of IP may be reduced, with approval from the Sponsor's Medical Monitor (or designee), to doses mentioned in Section 6.5.1. Subject must return weekly or more frequently for repeat liver chemistry tests (ALT, AST, GGT, ALP, total bilirubin, direct bilirubin, and INR) until the abnormalities resolve, stabilize or return to baseline. If at any time the subject meets liver chemistry interruption criteria (as specified in Table 7), then follow the instructions in “Liver Chemistry – Investigational Product Interruption Criteria” in Table 7 and in consultation with the Sponsor's Medical Monitor (or designee) initiate relevant assessment procedures.

^aNew or worsening symptoms believed to be related to liver injury (such as fatigue, nausea, vomiting, right upper quadrant pain or tenderness, or jaundice) or hypersensitivity (such as fever, rash or eosinophilia).

Table 7: Liver Chemistry Criteria Requiring Investigational Product Interruption and Additional Monitoring

Liver Chemistry – IP Interruption Criteria	
ALT/AST (single occurrence)	ALT or AST $\geq 5 \times$ ULN
ALT/AST	ALT or AST $\geq 3 \times$ ULN persists for ≥ 4 weeks
+ Bilirubin ^{a,b}	ALT or AST $\geq 3 \times$ ULN and bilirubin $> 2 \times$ ULN ($> 35\%$ direct bilirubin)
+ INR ^b	ALT or AST $\geq 3 \times$ ULN and international normalized ratio (INR) > 1.5 , if INR measured
+ Cannot Monitor	ALT or AST $\geq 3 \times$ ULN and cannot be monitored weekly for 4 weeks
+ Symptomatic ^c	ALT or AST $\geq 3 \times$ ULN associated with symptoms (new or worsening) believed to be related to liver injury or hypersensitivity
ACTIONS	

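### Protocol 6.5.1 tells sites to discontinue IP for confirmed Table 7 liver findings, whereas Table 7 and Section 7.1.3 prescribe interruption with possible restart

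*Protocol*

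**What the plan says.** Protocol 6.5.1 has two liver rules. ALT or AST from 3 to below 5 x ULN that meets Table 6 may lead to a dose reduction if the Medical Monitor approves. For confirmed values of at least 3 x ULN that meet Table 7, "IP should be discontinued". The section gives no route back to dosing after such a stop; its re-escalation rule covers only subjects whose dose was reduced.

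Appendix 7 describes the same subjects differently. Table 7 is titled "Liver Chemistry Criteria Requiring Investigational Product Interruption and Additional Monitoring". Its first action is "Immediately interrupt IP". Restart needs the Medical Monitor's approval and is then at a modified dose, for which the table refers back to 6.5.1. Only the refusal branch ends treatment: "If restart not granted, permanently discontinue IP". Section 7.1.3 agrees with the table, describing "temporary interruption of IP with possible restarting criteria and actions".

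One footnote sides with 6.5.1. Footnote a to Table 7 reads "If serum bilirubin fractionation is not immediately available, discontinue IP if ALT or AST" is at least 3 x ULN and bilirubin exceeds 2 x ULN. It concerns the bilirubin row alone, and only when the fractionated result is not at hand.

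**The concern.** One set of laboratory findings triggers two instructions in operative protocol text. Under one, the subject's treatment is over. Under the other, it is paused pending a decision.

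The two differ in what they lead to. Under Protocol 4.1.2, both routes into the OLE require the subject to be on IP, either at Week 36 or when the UC Disease Activity criteria are met. Within the OLE, permanent discontinuation means withdrawal from the study. SAP 9.1 tabulates adverse events leading to interruption separately from those leading to discontinuation. If sites act on different sections, the same liver finding can therefore end up in different tables.

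**Working it through.** The plan gives no figure to reproduce. The check is whether the two instructions can be reconciled, then which one is intended, then what the difference amounts to.

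**1. Could it be interrupt first, then discontinue once confirmed?** Section 6.5.1 applies to confirmed values, so this is the natural attempt. Table 7 says what to do on confirmation: "If the repeat liver chemistry test confirms the criteria are met, monitor the subject". It does not call for discontinuation at that point, and its restart provision is not limited to unconfirmed cases. This reading fails.

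**2. Could discontinued in 6.5.1 mean a temporary stop?** Sections 7.1.1, 7.1.2, 7.1.4 and 7.1.5 add the word permanently and 6.5.1 does not. On the other side, 6.5.2 uses the bare word for a stop that 7.1.5 makes permanent. Table 7 itself uses interrupt and permanently discontinue for two different actions. The vocabulary does not settle the question.

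**3. Which rule is intended?**

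- Section 7.1 and the opening of Appendix 7 send liver actions to 7.1.3 and Appendix 7, and dose modification to 6.5.1.
- SAP 7.3 attributes the permitted dose modifications to Protocol 6.5.1, counts prescribed interruption among them, lists liver chemistry abnormality as a reason and tabulates resumption. Section 6.5.1 contains no interruption rule, so the SAP assumes content that is missing from it.

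Both point to interruption. Neither removes the contrary sentence, and a site that follows Table 7's pointer for the restart dose arrives at the section containing it.

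**4. What differs for a subject?**

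| Confirmed Table 7 event | 6.5.1 taken literally as ending treatment | Table 7 followed |
|---|---|---|
| In the PCP, restart would be approved | IP ends; PCP visits continue; neither OLE route is open | IP resumes at a modified dose; OLE routes remain open |
| In the OLE, restart would be approved | IP ends; subject is withdrawn | IP resumes; subject stays in the OLE |
| Restart refused | IP ends | IP ends |

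The rules diverge only where the Medical Monitor would have agreed to restart.

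**5. Ceiling on treatment time.** Inputs: 36 PCP weeks and 24 OLE weeks, a maximum of 36 + 24 = 60.

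- Event at PCP Week 4: (36 − 4) + 24 = 56 weeks.
- Event at PCP Week 12: (36 − 12) + 24 = 48 weeks.
- Event at OLE Week 12: 24 − 12 = 12 weeks.

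Each assumes restart on the same day, and the PCP figures also assume a full OLE. Repeat testing, monitoring and approval make immediate restart unrealistic, so these are limits and not estimates.

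**The case against.** The strongest reply is that the conflict is nominal. Section 6.5.1 names Table 7, so its verb can be said to take its meaning from Table 7, just as the bare verb in 6.5.2 takes its permanence from 7.1.5. Table 7's pointer to 6.5.1 also works for its purpose, since the reduction steps are there. The Medical Monitor must be told within 24 hours and controls every restart, so a site is unlikely to act on 6.5.1 alone. Recording will follow what actually happens to dosing, whichever verb the site read.

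Much of this stands. It supports interruption as the intended rule, makes a wrong action less likely, and means the wording affects the adverse event tables only through what is done. It does not make 6.5.1 correct. A reader of that section finds a stop with no return, while Table 7 reserves permanent discontinuation for refused restarts.

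Three stronger readings are tempting and not supported:

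- **A safety hazard.** Dosing stops at once under both texts.
- **A bias in the primary endpoint.** SAP 8.1.4 counts discontinuation more than 28 days before the timepoint as failure and does not list interruption. With the Week 12 target at Day 85, that means a last dose before Day 57 (85 − 28). The path exists on paper, but without a rate of Table 7 events or of approved restarts, no effect can be claimed.
- **A general second conflict in footnote a.** It covers one row in one circumstance, and Appendix 2 makes fractionated bilirubin a routine test.

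**Conclusion.** The inconsistency is real, and Section 6.5.1 is wrong as written. The conclusion rests on current protocol text and on taking Section 7.1, Appendix 7 and SAP 7.3 as evidence of intent.

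The consequence is confined to subjects with a confirmed Table 7 finding for whom restart would have been approved. Each stands to lose further treatment and either OLE eligibility or OLE participation. How many there would be cannot be stated. The nearest figure, in Protocol 2.3.2, is liver function test elevation in 6% of the 32 GB004 subjects in the Phase 1 formulation study, without a multiple of ULN. The 56-week ceiling should not be read as an expected loss.

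A neighbouring gap is not part of this error. ALT or AST from 3 to below 5 x ULN with bilirubin above 2 x ULN and a direct fraction of 35% or less, with no other Table 7 criterion met, fits neither table. Section 7.1.3 still requires work-up of confirmed values, and Section 8 provides for Medical Monitor discussion of safety concerns. Only a defined action and timing are missing.

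**What to change.** In Protocol 6.5.1, change the second liver rule to: *IP should be interrupted; see Table 7 for restart or permanent discontinuation.* In Table 7 footnote a, change discontinue to interrupt for consistency.

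Optionally, add a row for the uncovered bilirubin pattern, using Table 6's notification within 24 hours and confirmation within 24 to 48 hours, with the Medical Monitor deciding on dosing.

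The cost is a one-line correction in 6.5.1 and one verb in the footnote, by protocol clarification or a letter to sites. Sample size, tests and the SAP do not change; the edit brings 6.5.1 into line with what SAP 7.3 already assumes.
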